##### **5.3.1.4. MMR, MR4.0 and MR4.5 at 3 month**

If a patient is missing the assessment, they will be coded as a non-responder.

##### **5.3.1.5. MMR, MR4.0 and MR4.5 at 6 and 9 months**

If a patient is missing a molecular response assessment at the time of interest and the patient demonstrates molecular response at both prior and subsequent visits, then that patient will be considered a responder at that time of interest. If a patient is missing molecular response at either prior or subsequent visits, then that patient will be considered a non-responder at that time of interest.

##### **5.3.1.6. MMR by 12 and 18 months (48 and 72 weeks)**

If a patient is missing a molecular response at the 48-week and 72-week visits and the patient has demonstrated a MMR at visits prior to the 48-week and 72-week visits, then the patient will be considered a responder by the 48-week and 72-week visits, respectively.

#### **5.3.2. Cytogenetic Response Assessment**

Handling of missing bone marrow data will take the following steps:

1. If bone marrow cytogenetics results are not available and a MMR is achieved on a specific date, then a CCyR response will be imputed for that date.
2. If bone marrow cytogenetics results are available where <20 metaphases analyzed with zero Ph+ cells and a MMR is achieved on a specific date, then a CCyR response will be imputed for that date.

#### **5.3.3. Hematologic Response Assessment**

Handling of missing hematology data will take the following steps:

1. For each patient, the observations are sorted by visit and the relative day.
2. For each observation, the peripheral blood differentials should add up to 100%. Some sites may not record 0%. Instead, the corresponding field may appear as missing or “ND.” If myelocytes, promyelocytes and myeloblasts in the blood differential are reported as missing or “ND,” the following rule will be applied. Each domain of the differentials will be summed together. If the total is between 98.5% and 101%, the missing values will be assigned 0%. Otherwise, the observation will be left as is and the record will also be reported as a data issue.
3. If CHR cannot be assessed due to one or more missing components of CHR, impute CHR if a patient has a MMR or a CCyR and all assessed components of CHR are within appropriate limits.

Furthermore, in the absence of extramedullary disease info, it is assumed that spleen is non-palpable.

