The investigator may schedule visits (unplanned visits) in addition to those listed in the SCHEDULE OF ACTIVITIES table in order to conduct evaluations or assessments required to protect the well-being of the patient.

Visit Identifier ^a	Screening		Core Treatment Phase													Extension Phase	End of Treatment / Withdrawal
	0	0	1	1	1	1	1	2	2	3	3	4	5	6	9, 12		
Month	0	0	1	1	2	3	4	6	8	10	12	16	20	24	36, 48	Every 12 weeks up to 2 years, then every 24 weeks thereafter	7-28 days after the last dose of study drug
Week	0	0	1	1	2	3	4	6	8	10	12	16	20	24	36, 48		
Day	-28 to registration	-14 to registration	1	7	14	21	28	42	56	70	84	112	140	168	252, 336		
Visit Time Window			±4 days													±1 week	
Informed consent	X																
Registration			X														
Inclusion/Exclusion criteria review	X																
Demographic data collection		X															
Sokal score calculation ^b		X															
Medical ^c /Cancer history ^d review		X															
Physical examination ^e		X				X		X		X					X	X	X
Vital signs, weight, and height (screening only) ^f		X	X							X				X	X	X	X
ECOG performance status		X								X						X	X
Extramedullary assessment ^g		X				X		X		X					X	X	X
Digital ECG ^h		X	X			X		X		X						As clinically indicated	
Chest X-ray		X								As clinically indicated							X
Contraception check ^l	X		X			X		X		X	X	X	X	X	X	X	X
ECHO or MUGA ^l	X									As clinically indicated							X

Visit Identifier ^a	Screening		Core Treatment Phase													Extension Phase	End of Treatment / Withdrawal
	0	0	1	1	1	1	1	2	2	3	3	4	5	6	9, 12		
Month	0	0	1	1	2	3	4	6	8	10	12	16	20	24	36, 48	Every 12 weeks up to 2 years, then every 24 weeks thereafter	7-28 days after the last dose of study drug
Week	0	0	1	1	2	3	4	6	8	10	12	16	20	24	36, 48		
Day	-28 to registration	-14 to registration	1	7	14	21	28	42	56	70	84	112	140	168	252, 336		
Visit Time Window			±4 days													±1 week	
Laboratory Tests																	
Hematology including CBC with differential ^k		X		X	X	X	X	X	X	X	X	X	X	X	X	X ^y	X
Chemistry panel with electrolytes and CK ^l		X				X		X		X		X	X	X	X ^y	X	
Liver function tests ^m		X				X		X		X		X	X	X	X ^y	X	
Estimated glomerular filtration rate		X				X		X		X		X	X	X	X ^y	X	
Coagulation panel ⁿ		X								X					X ^y	X	
HBV and HCV test		X															
Dipstick urinalysis (microscopic if abnormalities detected)		X				X				X					X ^y	X	
Serum or urine pregnancy test (for women of childbearing potential)	X		X			X		X		X	X	X	X	X	X ^y	X	

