- b. Every effort should be made in order to have Sokal score calculated prior to any anti-CML treatments (ie. at initial diagnosis of patient). Sokal formula is $Exp(0.0116 \times (age - 43.4) + 0.0345 \times (spln - 7.51) + 0.188 \times [(plt/700)^2 - 0.563] + 0.0887 \times (blasts - 2.1))$; Note: Spln=centimeters below costal margin, plt=platelet count, $10^9/L$, blasts=% blasts in peripheral blood. If the patient has already received anti-CML treatment prior to screening every effort should be made to obtain test results/data before the start of treatment in order to calculate the Sokal score. If patient did not have prior anti-CML treatment, the Sokal score will be calculated using data obtained at screening.
- c. Medical history review includes clinically significant past and current diagnoses (including complete cardiac history) and surgical procedures.
- d. Cancer history review includes full history of the course of the patient's cancer including date of diagnosis and any prior treatments, history of blood and platelet transfusions or history of lumbar punctures within 28 days prior to registration.
- e. Complete physical examination ensuring examination of liver and spleen will be performed.
- f. Vital signs include temperature (axillary), supine blood pressure, and heart rate. Height will be measured at screening only.
- g. Extramedullary assessment will include physical examination and based on this assessment and any specific evidence, appropriate imaging testing can be requested by the investigator. The assessment should be done at any time if extramedullary disease is suspected.
- h. Digital ECGs to be done in triplicate at each time point and should be performed at the same as PK sampling (if applicable). End of Treatment/Withdrawal visit ECG should be done at least 5 days after the last dose of bosutinib and prior to initiating other anticancer treatment (if possible). ECG should also be performed if clinically significant decrease in ejection fraction is detected by ECHO/MUGA while on treatment, and otherwise as clinically indicated.
- i. Male patients who are able to father children and female patients who are of childbearing potential will need to follow the contraception guidelines in Section 4.3.

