- j. ECHO or MUGA to be performed at screening (within 2 weeks prior to registration) and at End of Treatment/Withdrawal or at Week 96, whichever is earlier. If a patient has undergone ECHO or MUGA as standard of care prior to entering the study, the procedures will not have to be repeated if results are available and the procedures were performed within 28 days prior to registration. To enable meaningful clinical comparison, every effort must be made to ensure that the imaging method used to assess cardiac function remains consistent for each individual patient through the course of the trial.

- k. Hematology including automated complete blood count (CBC) (eg, hemoglobin, RBC, WBC, platelets and hematocrit) with differential counts (eg, neutrophils, lymphocytes, monocytes, eosinophils, basophils, metamyelocytes, myelocytes, promyelocytes, myeloblasts, unspecified blast cells and band cells) to be performed locally. Hematology assessments are to be performed at Screening, Weeks 1, 2, 3, 4, 6, 8, 10, 12, 16, 20, 24 and then every 12 weeks for the next 72 weeks (ie, until the end of Year 2), then every 24 weeks, and End of Treatment/Withdrawal visit. CHR must be confirmed by 2 assessments at least 4 weeks apart. Hematology to be repeated at least 4 weeks after achieving first CHR.
- l. Chemistry panel to be performed locally including: sodium, potassium, chloride, carbon dioxide or bicarbonate (if available), blood urea nitrogen (BUN) or urea, creatinine, glucose, total protein, albumin, calcium, alkaline phosphatase, amylase, lipase, phosphorous or phosphate, and magnesium. Creatine kinase (CK) also to be performed locally. Abnormally high CK values should be confirmed and fractionated (where possible). Uric acid to be obtained until patient achieves a CHR. Supplementation is advised for potassium levels or magnesium levels below the lower limit of normal (LLN), with consideration of the patient's underlying renal function.
- m. Liver Function tests to be performed locally including: total bilirubin, aspartate aminotransferase (AST) and alanine aminotransferase (ALT).
- n. Coagulation panel to be performed locally including: prothrombin time (PT) expressed as either PT or international normalized ratio (INR) and partial/activated partial thromboplastin time (PTT or aPTT).
- o. The first dose of study drug should occur no later than 3 business days after registration of the patient, with the day of first study drug administration = Day 1.

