Appendix 2. Response Definitions

A. Hematologic Responses to Treatment

Hematologic Responses	Definition
Complete Hematologic Response (CHR) had to meet all criteria	
 • WBC $\leq 10 \times 10^9/L$ • Basophils <5% in blood • No myelocytes, promyelocytes, myeloblasts in the blood differential • Platelet count $<450 \times 10^9/L$ • Spleen non-palpable^a

a. In a statistical analysis, if spleen disease was not assessed, it is assumed that spleen is non-palpable.

B. Cytogenetic Responses to Treatment

Before Treatment	Cytogenetic Responses (based on analysis of at least 20 metaphases)	% Philadelphia Chromosome Positive Cells
Chronic Phase	None	>95%
	Minimal	66-95%
	Minor	36-65%
	Partial	1-35%
	Complete	0%
	Major	Complete + Partial Rates

C. Molecular Responses to Treatment

Before Treatment	Molecular Response	RT-PCR (BCR-ABL Ratio)
Chronic Phase	Major, or MMR	≤0.1% (corresponding to ≥3 log reduction from baseline*) with a minimum number of ABL transcripts specified by the central laboratory
	MR ¹	A 1 log reduction in BCR-ABL transcript with a minimum number of ABL transcripts specified by the central laboratory
	MR ²	A 2 log reduction in BCR-ABL transcript with a minimum number of ABL transcripts specified by the central laboratory
	MR ^{4.0}	Either (i) Detectable disease with ≤0.01% BCR-ABL IS or (ii) Undetectable disease in cDNA with a minimum number of ABL transcripts specified by the central laboratory
	MR ^{4.5}	Either (i) Detectable disease with ≤0.0032% BCR-ABL IS or (ii) Undetectable disease in cDNA with a minimum number of ABL transcripts specified by the central laboratory in the same volume of cDNA used to test for BCR-ABL

* standardized baseline from central laboratory

D. Definitions of Blast Phase and Accelerated Phase

Patient meeting any of the following criteria:

Blast Phase	≥30% Blasts in blood or bone marrow Extramedullary blast proliferation, other than in spleen
Accelerated Phase	15-29% blasts in blood or marrow, or >30% blasts plus promyelocytes in blood or marrow with blasts <30%; ≥20% basophils in blood Persistent thrombocytopenia (<100 × 10 ⁹ /L) unrelated to therapy ^a Clonal chromosome abnormalities in Ph ⁺ cells (CCA/Ph ⁺), major route, on treatment ^b

a. In a statistical analysis, persistent thrombocytopenia is not considered to define AP progression as the database does not collect data regarding the relationship between the platelet value and therapy.

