### 3.2.4. EFS

The EFS is measured from the date of first dose until the first occurrence of one the following events, censored at the earlier of the last valid hematologic or cytogenetic assessment for those without events:

1. Death due to any cause;
2. Transformation to AP or BP (on treatment; see [Appendix 1.3](#));
3. Loss of CHR.
  - Loss of CHR is defined as the appearance of any of the following, confirmed by a second determination  $\geq 4$  weeks later (unless associated with CML-related treatment discontinuation):
    - WBC count that rises to  $>20.0 \times 10^9/L$ ;
    - Pplatelet count that rises to  $\geq 600 \times 10^9/L$ ;
    - Appearance of palpable spleen or other extramedullary involvement proven by biopsy;
    - Appearance of 5% myelocytes in the peripheral blood, or

- Appearance of blasts or promyelocytes in the peripheral blood.
4. Loss of CCyR (unless associated with CML-related treatment discontinuation; refer to [Section 3.2.3](#) for the definition of loss of CCyR), or
  5. For patients not achieving a CHR: doubling of white blood cell (WBC) at least 1 month apart with the second value  $>20 \times 10^9/L$  and maintained in subsequent assessments for at least 2 weeks.

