#### Appendix 1.4. Hematologic Responses

Hematologic Responses a	Definition
Complete Hematologic Response, or CHR	
 
• <math>WBC \leq 10 \times 10^9/L</math>.
 
• Basophils <math><5\%</math> in blood.
 
• No myelocytes, promyelocytes, myeloblasts in the blood differential.
 
• Platelet count <math><450 \times 10^9/L</math>.
 
• Spleen non palpableb.
 

- a. Had to meet all criteria indicated in the Definition column
- b. In the absence of extramedullary disease info, it is assumed that that spleen is non-palpable.

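### The rule that an unexamined spleen counts as non-palpable can credit CHR against the patient's own last spleen examination

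*SAP*

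**What the plan says.** CHR requires five criteria together: white cell count, basophils, no immature forms in the blood, platelets, and a spleen that cannot be felt (Protocol Appendix 2, Table A; SAP Appendix 1.4). Missing spleen information is handled in three places:

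- SAP 5.3.3: "in the absence of extramedullary disease info, it is assumed that spleen is non-palpable".
- SAP Appendix 1.4, footnote b: "In the absence of extramedullary disease info, it is assumed that that spleen is non-palpable".
- Protocol Appendix 2, Table A, footnote a: "In a statistical analysis, if spleen disease was not assessed, it is assumed that spleen is non-palpable".

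None of them says whether absence is judged per visit or per patient, or what happens when an earlier examination found the spleen palpable.

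In the protocol's Schedule of Activities, footnote k reads "Hematology assessments are to be performed at Screening, Weeks 1, 2, 3, 4, 6, 8, 10, 12, 16, 20, 24", with 12-weekly visits to the end of Year 2 after that. The spleen is examined at the physical examination; footnote e says "Complete physical examination ensuring examination of liver and spleen will be performed". That row, and the row "Extramedullary assessment ^g", carry far fewer marks than hematology.

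Protocol 7.1.1 requires a CHR to last at least 4 weeks and to be confirmed by two assessments at least 4 weeks apart. The SAP does not repeat this. For EFS, loss of CHR includes "Appearance of palpable spleen or other extramedullary involvement proven by biopsy" (SAP 3.2.4; likewise Protocol 9.2.2.4). It must be confirmed at least 4 weeks later unless tied to CML-related discontinuation of treatment.

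**The concern.** At most early visits the spleen is unassessed by design, not because data went missing. A palpable spleen at entry is also foreseen: the inclusion criteria exempt hepatosplenomegaly from the ban on extramedullary disease, and spleen size enters the Sokal score. The rule turns a planned gap in the schedule into evidence that one CHR criterion is met.

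It is also looser than its neighbors. For other missing CHR components, step 3 of SAP 5.3.3 imputes CHR only when the patient has an MMR or a CCyR; the spleen assumption needs no such support. SAP 6.3.4 and Protocol 9.3.1.4 present the CHR footnotes as restrictions added to the definition, yet this one relaxes it.

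At stake are cumulative CHR, which could count patients who never had one, and the loss-of-CHR component of EFS.

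**Working it through.** The plan gives no figure for this point, so there is none to reproduce. The check is a reading of the schedule followed by a worked course.

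**Visits without a spleen examination**

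- Hematology visits through Week 24: 11 (footnote k). With Weeks 36 and 48, the Core Phase has 13.
- The physical-examination and extramedullary rows are marked at screening, in three early columns, then at Weeks 36/48, in the Extension Phase and at End of Treatment. The three early marks share columns with the PK row, which footnote w dates to Days 28, 56 and 84 (after Day 1). They are therefore read as Weeks 4, 8 and 12.
- Through Week 24: 11 − 3 = 8 visits without an examination (Weeks 1, 2, 3, 6, 10, 16, 20, 24). Core Phase: 13 − 5 = 8.
- Sensitivity to the broken table: read literally, the early marks fall at Weeks 3, 6 and 10, again 11 − 3 = 8. If Week 24 also had an examination, 11 − 4 = 7. Weeks 16 and 20 are unexamined in all three readings.

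**Visit pairs that meet the 4-week rule with no examination at or between them**

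- Weeks 16 and 20: Day 140 − Day 112 = 28 days.
- Weeks 20 and 24: Day 168 − Day 140 = 28 days.
- Weeks 16 and 24: 168 − 112 = 56 days. With ±4-day visit windows this stays at 56 − 8 = 48 days or more, so the result does not depend on an exact 28-day gap (if Week 24 is unexamined).

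**Worked course: spleen still palpable, all other criteria met from Week 12**

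| Visit | Spleen examination | CHR under the stated rule | CHR with last examination carried forward |
|---|---|---|---|
| Week 12 | palpable | no | no |
| Week 16 | none scheduled | yes | no |
| Week 20 | none scheduled | yes, confirmed at 28 days | no |

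What follows depends on Weeks 36 and 48. If the spleen is then non-palpable, the patient reaches a true CHR and cumulative CHR is unchanged; only the date was early. If it is palpable at both (Day 336 − Day 252 = 84 days apart), the CHR was never real. If those findings are also counted as an appearance, EFS records a confirmed loss.

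**How wide the pattern is**

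Take every combination of the visit at which counts normalize and a later visit at which the spleen resolves (or never does): 91 courses, with the rule applied visit by visit.

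| Confirmation rule | False CHR | False CHR, then two later palpable examinations at least 4 weeks apart |
|---|---|---|
| No failing assessment in between (4-week duration kept) | 39 | 10 |
| Any two qualifying assessments at least 4 weeks apart | 60 | 23 |

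Under the stricter rule all 10 need a spleen palpable through Week 48. These are counts of patterns, not probabilities. With the last examination carried forward, both columns are zero in every course.

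**Size**

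One patient in 60 is 1/60 = 1.7 points. The documents do not give the number with a persistently palpable spleen and otherwise complete response. Assuming 0 to 5 such patients, the range is 0 to 5/60 = 8.3 points.

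**The case against.** The strongest reply is that the rule need not work visit by visit. Absence of information could mean that none exists for the patient, so a recorded palpable spleen would never be overridden. The text allows that reading. But SAP 5.3.3 sorts and processes individual observations, which favors the visit-level reading, and nothing there protects a palpable spleen recorded at a previous visit. The call in footnote g for an extramedullary assessment on suspicion does not help either: it does not carry a known palpable spleen forward. Protocol 7.1.1 also asks for clinical exclusion of extramedullary disease before CHR; that shows the intent, but the imputation rule bypasses it.

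Several objections stand and limit the point:

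- A reader might infer that Weeks 2/6 and 6/10 also yield a confirmed CHR. On the aligned schedule the Week 4 and Week 8 examinations fall between them, and a palpable spleen there breaks the 4-week duration in Protocol 7.1.1.
- A reader might infer that persistent splenomegaly will produce a false EFS event. The criterion speaks of appearance, which need not cover a spleen already known to be palpable, and it is unclear whether the biopsy condition applies to the spleen.
- A reader might set the 2% progression and 3% death from the earlier first-line Phase 3 study (Protocol 1.2.3) against a few false losses and conclude that the EFS event count could double. EFS also counts loss of CHR, loss of CCyR and white-cell doubling, so that baseline is too low. The share with splenomegaly at entry is not given, and it would overstate the group affected in any case.
- CHR is exploratory, no time-to-CHR endpoint is planned, and EFS is not tested (SAP 5.1).

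**Conclusion.** The point holds in a limited form. Followed as written and visit by visit, the rule can credit a confirmed CHR at Weeks 16/20 to a patient whose last examination, at Week 12, showed a palpable spleen, with the 4-week duration requirement satisfied.

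Cumulative CHR can be too high, but only for patients who never reach a true CHR; for the others the response is merely dated early. A false loss of CHR in EFS is possible, not established. The direction of any EFS effect is not fixed either: an unexamined confirming visit could hide a real loss, and a false CHR removes the patient from the white-cell-doubling criterion reserved for those without a CHR. The number of patients affected is unknown. MMR at 12 months is unaffected.

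The conclusion rests on aligning a broken schedule table to the PK days and on the visit-level reading of the rule. The Week 16/20 gap survives the alternative readings of the table.

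**What to change.** Replace the assumption in SAP 5.3.3, SAP Appendix 1.4 footnote b and Protocol Appendix 2 Table A footnote a with three statements for the statistical derivation:

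1. At a hematology visit without a spleen examination, use the most recent examination result, screening included.
2. Assume a non-palpable spleen only when no examination has ever recorded a palpable one. This also covers a patient with no examination at all.
3. In EFS, count a palpable spleen as loss of CHR only if the most recent earlier examination was non-palpable, or if no earlier examination recorded a palpable spleen.

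Repeat the 4-week CHR duration and confirmation rule in the SAP, so that the derivation does not depend on the protocol alone. Section 9 of the protocol lets the SAP modify analyses other than the primary, so a SAP amendment can carry the change. The investigators' treatment-failure criteria in Protocol 6.5 are not touched.

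The cost is wording and programming on data already collected. The downside is that a spleen that resolves between examinations is credited only at the next one, so CHR may be dated later and the rate may be slightly lower.

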#### **5.3.4. Time-to-Event Data**

The primary missing data handling method will be censoring. A patient withdrawing from the study without experiencing the event of interest will be censored at the last valid (ie, evaluable) assessment of that event. A patient who fails on treatment, after missing two or more assessments of both hematologic and cytogenetic response, will be censored for on-treatment EFS at the last hematologic or cytogenetic assessment. A patient, who dies after treatment discontinuation during long-term follow-up and after missing two or more long-term follow-up assessments, will be censored for off-treatment EFS at the last assessment at which the patient was found to be alive and event-free. See also [Section 3.2.3](#) for duration of MMR or CCyR.

